10.8. Subgroup Analysis

Subgroup analyses will be performed as appropriate, due to either imbalance randomization in baseline subject demographics and/or clinical relevance to primary and secondary PK analyses and safety analysis. Factors including, but not limited to, age, race, and sex will be considered. Subgroups will be defined based on population median.

10.9. Determination of Sample Size

Statistical calculations indicate a minimum of 73 subjects per group is necessary. To allow for subject withdrawals or unevaluable data, approximately 81 subjects will be enrolled per group.

This study is powered based on a one-sided test with an overall study α of 0.05. A total of 162 subjects will be randomized to achieve 85% power with a one-sided significance level of 0.025.

This computation accounts for an expected 10% dropout rate resulting in 146 evaluable subjects. The following table outlines the underlying assumptions:

Table 7: The underlying assumptions

	Day 14 \geq 0.5 IU/mL
Non-inferiority margin	10%
Difference	0%
% success	98%

10.10. Interim Analysis

An interim analysis is not planned.

11. INVESTIGATOR'S STATEMENT**A Prospective, Randomized, Double-Blind, Parallel-group, Non-inferiority
Phase II/III Study of the Safety and Effectiveness of BPL HRIG With
Co-administration of Active Rabies Vaccine in Healthy Subjects****Study Code: RIG01****Version 1.0
Date: 26 Oct 2017**

I have carefully read this protocol and the clinical investigator's brochure and I confirm that they contain all the information necessary to perform the study I agree to carry out the study in compliance with the protocol, ICH GCP and applicable regulatory requirements.

Signature: _____ Date: _____

Principal Investigator

Name: _____
(Printed)

APPENDIX A. - ADVERSE EVENT DEFINITIONS AND REPORTING PROCEDURES

1. ABBREVIATIONS

ADR	- Adverse Drug Reaction
AE	- Adverse Event
BPL	- Bio Products Laboratory Limited
CRF	- Case Record Form
CRO	- Contract Research Organisation
eCRF	- Electronic Case Record Form
ECG	- Electrocardiogram
FDA	- Federal Drug Agency
ICF	- Informed Consent Form
IEC	- Independent Ethics Committee
IRB	- Institutional Review Board
IMP	- Investigational Medicinal Product
SAE	- Serious Adverse Event
SmPC	- Summary of Product Characteristics
SUSAR	- Suspected Unexpected Serious Adverse Reaction

2. DEFINITIONS OF ADVERSE EVENTS

2.1 Adverse Event (AE)

An adverse event is any untoward medical occurrence in a patient or clinical investigation subject administered a pharmaceutical product that does not necessarily have a causal relationship with this treatment. An adverse event can therefore be any unfavourable and unintended sign including an abnormal laboratory (or vital sign, ECG, etc.) finding, symptom or disease temporally associated with the use of study medication. All adverse events, whether considered by the investigator to be related to study medication must be described and recorded on the appropriate Adverse Event forms in the CRF/e-CRF. Where possible, a diagnosis should be made. Anticipated fluctuations of pre-existing conditions, including the disease under study that does not represent a clinically significant exacerbation or worsening need not be considered AEs.

2.2 Adverse Events Temporally Associated with the Injection

Unless clearly attributable to other causes any AEs that occur from the injection until Day 3 after the injection will be recorded as temporally related to the injection.

2.3 Clinical Laboratory and Other Adverse Events

If a laboratory result is considered by the investigator to be clinically significant or have a clinically significant pathological change from baseline it should be recorded as an AE.

Other abnormal results (e.g. x-rays, scans, physical examination findings) that worsen from baseline and/or are considered clinically significant should also be recorded as AEs.

The investigator will exercise his or her medical and scientific judgment in deciding whether an abnormal laboratory finding or other abnormal assessment is clinically significant.

AEs should be reported and documented in accordance with the procedures outlined below. All AEs occurring during the study must be documented on the relevant CRF/e-CRF pages. The following data should be documented for each AE:

- Description of the symptom event
- Classification of 'serious' or 'not serious'
- Severity
- Date of first occurrence and date of resolution (if applicable)
- Action taken
- Causal relationship
- Outcome of event (unknown, recovered, not recovered, recovered with sequelae, death [with date and cause reported])

2.4 Pregnancy

Subjects will be instructed that known or suspected pregnancy occurring during the study should be reported to the investigator. The investigator should also be notified of pregnancy occurring during the study but confirmed after completion of the study. If a subject is found to be pregnant after inclusion in the study, the subject must be withdrawn from the study. Any pregnancy will be followed to term and the status of mother and child will be reported to the Sponsor after delivery.

Full details of any pregnancy will be recorded on the AE page of the CRF/eCRF, and a Pregnancy & Outcome Report Form will be completed. A copy of the Pregnancy Report Form must be completed and faxed to the appropriate contact (as detailed in the Study Reference Manual (SRM)) within 24 hours.

2.5 Adverse Drug Reaction (ADR)

All noxious and unintended responses to a medicinal product related to any dose administered. The phrase 'response to a medicinal product' means that a causal relationship between a medicinal product and an adverse event is at least a reasonable possibility.

2.6 Serious Adverse Event (SAE) or Drug Reaction

A **Serious Adverse Event or reaction** is any untoward medical occurrence that at any dose:

- **results in death,**
- **is life-threatening (patient at risk of death at time of event; not hypothetically life-threatening),**
- **requires inpatient hospitalization or prolongation of existing hospitalisation,**
- **results in persistent or significant disability or incapacity,**
- **is a congenital anomaly or birth defect?**
- **is an important medical event (see below for definition)?**

The term “life-threatening” in the definition of “serious” refers to an event in which the patient was at risk of death at the time of the event; it does not refer to an event which hypothetically might have caused death if it were more severe.

Medical and scientific judgement must be exercised in deciding whether expedited reporting is appropriate in other situations, such as important medical events that may not be immediately life-threatening or result in death or hospitalization but may jeopardize the patient or may require intervention to prevent one of the other outcomes listed in the definition above. These should also usually be considered serious.

Examples of such events are intensive treatment in an emergency room or at home for allergic bronchospasm; blood dyscrasias or convulsions that do not result in hospitalisation; or development of drug dependency or drug abuse.

The following medical conditions will be automatically regarded as serious, regardless of the classification assigned by the clinical trial investigator reporting the case:

- Anaphylaxis or anaphylactoid reaction
- Myocardial infarction
- Stroke
- Pulmonary embolism
- Infection with any blood borne virus
- Any transmissible spongiform encephalopathy

In general, information that might materially affect the risk-benefit assessment of a medicinal product or that would suggest changes in the way it is to be administered or to the way a clinical investigation should be conducted should be reported in an expedited manner. Examples include:

- Single case reports of an expected adverse reaction with an unexpected outcome e.g. fatal outcome
- For an expected serious adverse reaction, an increase in the rate of occurrence which is judged to be clinically important.

- A significant hazard to the patient population, such as lack of efficacy in treating life-threatening diseases or an event which is significant enough to lead to important changes in the way a medicine is developed e.g. change in dose, monitoring, consent forms.
- A major new safety finding from a newly completed animal study.
- A serious adverse event associated with a study procedure that could modify the conduct of the trial.

2.7 Unexpected ADRs

An adverse reaction, the nature or severity of which is not consistent with the applicable product information (e.g. Investigator's Brochure for an unapproved investigational product or summary of product characteristics (SmPC) for an authorised product). Reports which add significant information on specificity, severity or frequency about a listed ADR would be classed as 'unexpected', for example, a report of interstitial nephritis when acute renal failure is the listed ADR or a report of fulminant hepatitis when the product information only lists hepatitis.

Expectedness for BPL HRIG will be assessed against the Investigator's Brochure, for HyperRAB[®] will be assessed against the USPI ([Appendix D](#)) and rabies vaccine will be assessed against the USPI ([Appendix E](#)).

2.8 Suspected Unexpected Serious Adverse Reactions (SUSARs)

All suspected adverse reactions related to an IMP (the tested IMP, comparators or active vaccine) which occur that are both unexpected and serious (SUSARs) are subject to expedited reporting. BPL and / or the designated CRO will be responsible for reporting these to the concerned Competent Authorities and to the Ethics Committee concerned, as detailed in the Study Reference Manual.

3. DETECTING ADVERSE EVENTS

Subjects will be carefully monitored for adverse events that occur after the Informed Consent Form (ICF) has been signed until the last day of the study. The Investigator or delegate will question the subjects about adverse events using a non-leading question such as "How are you feeling?" The Investigator will also record adverse events reported spontaneously by the subjects. **Clinically significant** changes in the findings of physical examination, and clinically significant abnormalities in the result of objective tests (e.g. laboratory variables, ECG) should be recorded as AEs.

3.1 Causality

All AEs will be recorded in the CRF/eCRF, whether considered to be related or unrelated to the treatment. The record will include the following: brief description of event (preferably a diagnosis), date and time started and stopped severity, outcome, actions taken and classification of the AE. The Investigator should also evaluate the probability of a causal relationship of the AE to each medication administered during the study according to the following criteria as:

-
1. Unrelated Clinical event with an incompatible time relationship to study medication administration, or that could be explained by underlying disease or other drugs or chemicals, or is incontrovertibly not related to the IMP.
 2. Unlikely Clinical event whose time relationship to study medication administration makes a causal connection improbable, but that could plausibly be explained by underlying disease or other drugs or chemicals.
 3. Possible Clinical event with a reasonable time relationship to study medication administration, but that could also be explained by concurrent disease or other drugs or chemicals.
 4. Probable Clinical event with a reasonable time relationship to study medication administration, and is unlikely to be attributed to concurrent disease or other drugs or chemicals.
 5. Very likely / certain Clinical event with plausible time relationship to study medication administration, and that cannot be explained by concurrent disease or other drugs or chemicals.

Study medication is defined as those investigational compounds or their controls and vaccines used in the study.

It will be assumed that for all adverse events classified as “probably related”, “possibly related” or “very likely / certainly related” to the study medication, there is reasonable likelihood that the adverse event was causally related to the product. All such adverse events will be regarded as “causally related” to the study medication.

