6. INVESTIGATIONAL AND AUXILIARY MEDICINAL PRODUCTS

In this study, 'study medication' is defined as all products administered: BPL HRIG, comparator HRIG, and active rabies vaccine.

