10.6.1. Adverse Events

Adverse events (AEs) will be reported by the MedDRA system organ class and preferred term. Only treatment-emergent AEs, defined as those events with onset date from dosing with BPL HRIG / vaccine or comparator HRIG / vaccine will be included in the summary tables. All AEs will be included in the data listings.

Treatment-related AEs will be defined as events recorded as having a possible, probable or very likely/certain causality to treatment. AEs leading to withdrawal will be defined as events where the subject's participation in the study was discontinued as a result of the AE.

AEs will be summarized descriptively for all subjects and by treatment group. The denominator used for the calculation of percentages will be the number of subjects in the safety population per treatment group. For all AE summaries described below, counting will be performed by subject and event. For counts by subject, subjects experiencing the same event more than once

will have that event counted only once within each system organ class and once within each preferred term.

The following summaries of treatment-emergent AEs will be provided:

Summary of AEs

- 1) The number and percentage of subjects reporting AEs, serious AEs, study medication related AEs, AEs leading to withdrawal and AEs leading to death.
- 2) The number of AEs, serious AEs, study medication-related AEs, AEs leading to withdrawal and AEs leading to death.

Summary of AEs by Severity of Event

The number and percentage of subjects reporting AEs, and study medication-related AEs, will be summarized by the system organ class and by the preferred term. The severity of event will be recorded once per subject for each term as the maximum severity experienced by each subject (i.e. where the order of most severe to least severe is given by: severe, moderate and then mild).

Summary of AEs by Causality

The number and percentage of subjects reporting AEs will be summarized by the system organ class and by the preferred term. The causality will be recorded once per subject for each term giving the most likely relationship to study medication (i.e. in the order: very likely/certain, probable, possible, unlikely and then unrelated).

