5. REPORTING SERIOUS ADVERSE EVENTS

When an Adverse Event occurs, which fulfils the definition of serious (see Section 2.6 for definition) the Investigator must complete and sign the serious adverse event form and send it within 24 hours to the appropriate contact.,

Medical cover for urgent queries relating to adverse events will be provided on 24 hours / 7 days a week by the following:

[REDACTED]

All SAE reports must be e-mailed or faxed directly to [REDACTED] at [REDACTED] or [REDACTED] (see study reference manual for guidance on providing documentation of SAE).

The Investigator is responsible for expedited reporting of all Serious Adverse Events immediately to BPL and / or the designated CRO except for those that the protocol or Investigator's Brochure identifies as not requiring immediate reporting. This reporting requirement covers any serious adverse events that develop at any point between the date when a subject provides informed consent and up to 28 days after the last administration of the investigational medicinal product (HRIG or rabies vaccine). The investigator is also responsible for reporting to BPL and / or the designated CRO any serious adverse events with an onset date more than 28 days after the last administration of the product if he/she judges the serious adverse event to be possibly, probably or very likely/certainly related to the product.

The immediate report should contain the following as a minimum:

- a suspected investigational medicinal product
- study subject number
- details of the serious adverse event
- classification of SAE
- causality of SAE (if available)

The immediate SAE form should be followed by a detailed, complete SAE form as soon as possible. The immediate report and follow-up reports shall identify subjects by unique code numbers assigned to the latter.

Adverse events and/or laboratory abnormalities identified in the protocol as critical to the evaluation of safety must be reported to BPL and / or the designated CRO by the Investigator according to the reporting requirements within the time periods specified in this protocol.

The investigator must not wait to receive additional information to document fully the event before notification of a SAE, though additional information may be requested. Where applicable, information from relevant laboratory results, hospital case records and autopsy reports should be obtained.

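### As worded, the causality grade Unrelated contains the grades Possible and Unlikely, so one well-timed event can correctly be coded either treatment-related or not

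*Protocol*

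**What the plan says.** Protocol Appendix A, section 3.1, asks the investigator to "evaluate the probability of a causal relationship of the AE to each medication administered during the study" on a five-grade scale. The grades are built from timing and from whether something else could account for the event.

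- *Unrelated*: timing incompatible, "or that could be explained by underlying disease or other drugs or chemicals, or is incontrovertibly not related to the IMP".
- *Unlikely*: timing that "makes a causal connection improbable, but that could plausibly be explained by underlying disease or other drugs or chemicals".
- *Possible*: reasonable timing, "but that could also be explained by concurrent disease or other drugs or chemicals".
- *Probable*: reasonable timing, and another cause is unlikely.
- *Very likely/certain*: plausible timing, and no other cause can explain the event.

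The line that matters in analysis runs between *Unlikely* and *Possible*. Protocol 10.6.1 states: "Treatment-related AEs will be defined as events recorded as having a possible, probable or very likely/certain causality to treatment". SAP section 8h repeats this. For serious events starting more than 28 days after the last dose, Appendix A section 5 asks for a report "if he/she judges the serious adverse event to be possibly, probably or very likely/certainly related to the product".

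On the vaccine's status, Appendix A 3.1 says: "Study medication is defined as those investigational compounds or their controls and vaccines used in the study". Protocol section 6 likewise counts the vaccine as study medication. Neither place says what *other drugs* means when a single product is being rated.

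**The concern.** A grading scale should give each event one grade. Here the conditions for *Unrelated* are joined by *or*, so an available alternative explanation is enough by itself, even when the timing fits. The same facts define *Possible*. Two investigators applying the text correctly can therefore put the same event on opposite sides of the related/not-related line.

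Three outputs depend on that line:

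- the related-AE counts, the related-AE severity table and the causality table (Protocol 10.6.1, SAP 8h);
- whether a serious event is a suspected reaction for SUSAR purposes (Appendix A 2.8), and whether the sponsor expedites it, which Appendix A section 5 ties to the investigator's opinion of relatedness;
- whether the investigator must report a late SAE at all.

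Protocol 2.5 and 2.6 say that BPL HRIG has had no clinical trials and that trial data on the frequency of its undesirable effects are not robust. Related-event data from this study will therefore carry weight.

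**Working it through.** The plan gives no figure to reproduce, so the check is logical. I crossed timing (incompatible, improbable, reasonable) with alternative explanation (could explain, unlikely to explain, cannot explain) and applied each written definition. Plausible timing, the term used in the top grade, is treated as reasonable timing.

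| Timing | Alternative cause | Grades met as written | After the fix below |
|---|---|---|---|
| Incompatible | could explain | Unrelated | Unrelated |
| Incompatible | unlikely to | Unrelated | Unrelated |
| Incompatible | cannot | Unrelated | Unrelated |
| Improbable | could explain | **Unrelated and Unlikely** | Unlikely |
| Improbable | unlikely to | **none** | to be assigned |
| Improbable | cannot | **none** | to be assigned |
| Reasonable | could explain | **Unrelated and Possible** | Possible |
| Reasonable | unlikely to | Probable | Probable |
| Reasonable | cannot | Very likely/certain | Very likely/certain |

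Of the 9 combinations, 5 meet exactly one grade, 2 meet two and 2 meet none (5 + 2 + 2 = 9). *Unrelated* covers 3 + 1 + 1 = 5. The single *Possible* combination and the single *Unlikely* combination both lie inside it. Only the *Possible* overlap changes related status, because *Unlikely* and *Unrelated* both count as not related.

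Two points on the reading:

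- *Unrelated* and *Unlikely* speak of underlying disease, the other grades of concurrent disease, and neither term is defined. I treat them as the same. If they differ, *Possible* is contained only for events with a drug or chemical explanation, where the wording is identical. *Unlikely* stays contained either way.
- The table leaves out the third condition of *Unrelated* (incontrovertibly not related). A well-timed event of that kind could also meet *Possible*, so an order of precedence is needed.

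**Late SAEs.** Inputs: last vaccine dose nominally Day 28 (Appendix G), a 28-day reporting period regardless of causality (Appendix A section 5), end of study Day 140.

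- End of the unconditional period: 28 + 28 = Day 56.
- Remaining follow-up: 140 − 56 = 84 days, and 84 / 140 = 60% of the period after Day 0.

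This assumes all five vaccine doses at nominal times. A subject who stops vaccine early reaches the conditional period sooner. Protocol 2.9 justifies the 20 weeks partly as safety follow-up over five half-lives.

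**Vaccine as an alternative cause.** HRIG and vaccine are given at the same Day 0 visit (Protocol 7.3.2). Their listed reactions overlap, for example fever, headache, fatigue, malaise and injection-site pain, erythema and induration (Protocol Table 3 and 2.8). The instruction to rate each medication allows vaccine to be treated as an *other drug* when HRIG is rated. The definitions of study medication allow the opposite. The text does not settle it.

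**The case against.** A reader might infer that, because every subject also receives vaccine, nearly any early AE can be coded unrelated to HRIG, and that the comparison of the two HRIG products under Objective 4 is therefore biased. The documents do not support this.

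- Treating vaccine as an *other drug* is only one reading. Vaccine is defined as study medication, and the scale sets study medication against other drugs, so non-study drugs is a natural meaning.
- Even on the first reading, the event can be rated *Possible* or higher for vaccine. It then stays in the study-medication-related tables and remains eligible for SUSAR reporting, which covers vaccine (Appendix A 2.8). What can be lost is attribution to HRIG.
- Objective 4 compares two arms that receive the same vaccine, with safety assessed by blinded staff. AEs and SAEs are tabulated by arm whatever their causality.
- Injection site reactions are recorded separately and summarized by product without this scale (Protocol 8.2.2 and 10.6.2).
- Early SAEs are reported regardless of causality. AEs up to Day 3 are flagged as temporally related unless clearly due to something else (Appendix A 2.2).

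These points stand, and they limit the reach of the problem. They do not remove the overlap, which needs no assumption about vaccine: a concomitant drug is enough. The Day 3 flag sets no causality grade. The definition of an adverse drug reaction as at least a reasonable possibility (Appendix A 2.5) points investigators toward *Possible*, but does not change the conflicting definition. Appendix A section 5 also asks for reports of deaths and events of major concern at any later time, but only if the investigator links them to the study.

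HRIG-specific attribution also has a consequence of its own. Expectedness is judged product by product (Appendix A 2.7), so an event unexpected for HRIG but expected for vaccine could cease to qualify as a SUSAR if it is attributed to vaccine alone.

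**Conclusion.** The scale is wrong as written and should be corrected. The exposure is confined to outputs that use causality. Late SAEs would still be recorded in the CRF and tabulated; what is at risk is the report to the sponsor. Safety analysis is descriptive and the primary endpoint is not involved.

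No shift in the related-AE rate can be calculated. The documents give neither the expected frequency of well-timed events with an alternative explanation nor how investigators would choose between the overlapping grades. Any percentage would only restate its own assumptions. Moreover, if vaccine were the alternative cause, such a percentage would wrongly remove events that remain related through vaccine.

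The conclusion rests on reading the three conditions of *Unrelated* as true alternatives, which is what their grammar says, and on the reading of *disease* given in the working.

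**What to change.** In Appendix A 3.1:

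1. Delete the stand-alone alternative-explanation condition, so that *Unrelated* means incompatible timing or incontrovertibly not related. Joining that condition to incompatible timing by *and* would not do: an event with incompatible timing and no identified cause, such as one before dosing, would have no clear grade.
2. State that reasonable timing with an alternative explanation is *Possible*, and that incontrovertibly not related takes precedence where both could apply.
3. Assign a grade to improbable timing with no likely alternative cause, so that the five grades are mutually exclusive and exhaustive. Use one term for disease throughout.
4. State that the co-administered study product alone is not grounds for rating the other product *Unrelated*.

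Carry the same wording into the eCRF completion guide before ratings are made. The rule in Protocol 10.6.1 and SAP 8h for which grades count as related can stay. The cost is a wording change in two places, and possibly somewhat more events classed as related.
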